12.0 Data Management

Statistical Analysis Plan and Sample Size Justification for Aims 1 and 2

The primary outcomes in Aim 1 are serum antibody levels and functional antibody response measured using the OPA response at baseline and 30 days post-PVC₁₃ vaccine measured in the five groups defined in Table 1. The primary outcomes in Aim 2 are absolute number and proportion of B-cells phenotype specific to PPS₁₄, 19A, and 23F at baseline and 7 days post-PVC₁₃ vaccine measured in the same five groups. Comparisons between groups and within group between times for each aim will be evaluated using a linear

mixed model (LMM) approach. **The models will include fixed effects for participant group (65-75 RT, 35-45 RT, 65-75 DM/HTN, 65-75 healthy, and 35-45 healthy) and for time (day 0 or 30) and a random subject effect to account for repeated measures of antibody levels within participant.** Model assumptions will be checked graphically and transformations will be considered when necessary. Comparisons for each outcome between groups and within group between times will be evaluated using a series of contrasts from the LMM. **We are presenting power calculations for a range of assumptions to demonstrate that we anticipate having sufficient power to detect observed differences for all comparisons even if we fail to meet the recruitment target.** For power calculations we estimated the effect sizes for sample sizes ranging between 10 to 40 participants per group measured at 2 times at 80% and 90% power using a two-sided test assuming within subject correlation of 0.5 and Bonferroni adjusted and unadjusted significance

Figure 7: Effect sizes for different sample sizes, power, and significance

levels of $p = 0.005$ and 0.05 respectively. We will also evaluate the correlation between serum antibody levels and B cell count with OPA response across all participant groups using an LMM approach where OPA response is the dependent variable and antibody level or B-cell count is the independent variable. The model will include a random subject effect to account for repeated measures in the same subject. We anticipate good correlation (between 0.6-0.99), thus the objective is to estimate the correlation and define the level of precision around that correlation. A sample size of 200 subjects, 40 per group, provides >80% power to detect weak correlations of $r = 0.20$ and allows us to estimate a 95% confidence interval around the correlation to within ± 0.14 .

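### The plan promises a correlation with its precision, but the model it names returns a slope in assay units, and ±0.14 is a worst case near r = 0 that does not describe the anticipated 0.6 to 0.99

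*Combined protocol and SAP*

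**What the plan says.** The point lies in Section 12.0, Statistical Analysis Plan and Sample Size Justification for Aims 1 and 2.

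- **Objective.** The correlation is expected to lie between 0.6 and 0.99, "thus the objective is to estimate the correlation and define the level of precision around that correlation".
- **Analysis.** The association is to be evaluated over the five groups together, "using an LMM approach where OPA response is the dependent variable and antibody level or B-cell count is the independent variable". On the remaining structure the plan says only: "The model will include a random subject effect to account for repeated measures in the same subject". For this model, unlike the group-comparison model just before it, no fixed effect for group or time is named.
- **Planning figures.** With 40 subjects in each of the five groups (200 in all), the plan puts power above 80% at r = 0.20. It introduces the precision claim with the words "allows us to estimate a 95% confidence interval around the correlation to within"; the margin it then gives is ±0.14. The plan does not say at which r the ±0.14 applies.

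Two other sections bear on this. In Section 1.0, Aims 2 and 3 speak of correlating their measures with functional antibody activity after immunisation. Section 10.0 (Timing of blood samples) assigns flow cytometry to days 0 and 7, and antibody and OPA assays to day 0, day 30 and the yearly samples.

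**The concern.** A regression of OPA on antibody level estimates the change in OPA per unit of antibody. That number depends on the units and spread of both assays, and it is not a correlation. The section gives no route from one to the other: no standardisation, bivariate model, repeated-measures correlation or R-squared measure, and no interval method. An analyst who follows the text arrives at a slope and its standard error, not at the quantity the objective names.

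The missing terms matter as well. Repeated measures mix samples from before and after vaccination. If antibody and OPA both rise after the vaccine, pooled data show an association even when, at a given visit, people with more antibody have little more functional activity. Differences between group means act in the same way. A random subject effect does not remove a shift shared by all subjects. For B-cell counts the post-vaccination pair is not defined at all, because counts are taken at day 7 and OPA at day 30.

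Finally, the precision figure does not tell the reader what to expect over the range the plan itself anticipates.

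**Working it through.** **Inputs.** From Section 12.0: n = 200 (40 in each of five groups), r = 0.20 for power, ±0.14 for the interval, anticipated r of 0.6 to 0.99. The significance level for the correlation is not stated. I assume two-sided 0.05, the unadjusted level in the same paragraph.

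**Step 1: reproduce the plan's figures.** On the Fisher z scale, SE = 1/√(200 − 3) = 1/√197 = 0.0712.

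- Power at r = 0.20: Φ(atanh(0.20) × √197 − 1.96) = Φ(0.2027 × 14.04 − 1.96) = Φ(0.886) = 81.2%. The claim of more than 80% reproduces. At two-sided 0.005 the power would be 51.5%.
- Interval at r = 0: tanh(1.96 × 0.0712) = 0.139. The ±0.14 reproduces. At r = 0.20 the half-width is 0.133, with a lower arm of 0.137.

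Both figures are therefore those of a simple correlation in 200 independent pairs, not of the mixed model.

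**Step 2: the interval at the anticipated values.** CI = tanh(atanh(r) ± 1.96/√197):

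| r | 95% CI | Half-width |
|---|---|---|
| 0.6 | 0.503 to 0.682 | 0.089 |
| 0.8 | 0.744 to 0.845 | 0.051 |
| 0.9 | 0.870 to 0.923 | 0.027 |
| 0.99 | 0.987 to 0.992 | 0.003 |

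The half-width falls as r rises, so 0.139 is the largest it can be at n = 200.

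**Step 3: does the slope identify the correlation?** For y = bx + e, r = b·SDx / √(b²·SDx² + SDe²). Hold b = 1:

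- SDx = 1, SDe = 0.5: r = 1/√1.25 = 0.89
- SDx = 1, SDe = 1.33: r = 1/√2.77 = 0.60
- SDx = 2, SDe = 1.33: r = 2/√5.77 = 0.83

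Random-intercept mixed models fitted to simulated data with these settings (2,000 subjects, two visits) gave slopes of 1.00, 0.99 and 0.98 with correlations of 0.90, 0.61 and 0.82. The slope stays put while the correlation moves across the plan's expected range.

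**Step 4: effect of pooling visits.** This is an illustration with assumed values. Take equal numbers before and after vaccination, unit SD within a visit, within-visit correlation ρ, and both means rising by d SD. Then pooled r = (ρ + d²/4)/(1 + d²/4).

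- ρ = 0.2, d = 1: (0.2 + 0.25)/(1 + 0.25) = 0.36
- ρ = 0.2, d = 2: (0.2 + 1)/(1 + 1) = 0.60

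A weak correlate can thus reach the lower end of the anticipated range purely because both measures respond to the vaccine. The documents give no size for the rise, so this shows the mechanism and is not a forecast.

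**The case against.** The strongest reply is that the precision statement is correct. Within ±0.14 is an upper bound, and Step 2 shows that it holds at every r. A reader might infer that the figure is wrong, or too wide by the ratio of 0.14 to the half-widths in the table. The text does not support that: it never ties ±0.14 to 0.6 to 0.99, and it sits in the same sentence as the r = 0.20 power claim, where it reproduces. Likewise r = 0.20 is offered as a weak correlation still detectable, so its lying outside the expected range is no fault. This part of the reply stands in full.

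A second reply is that a correlation can be obtained from a mixed model by standardising, by a bivariate form or by a repeated-measures correlation, so it is too much to say that the analysis cannot deliver one. That also stands. What remains is that no such step is stated, and the possible routes answer different questions (between subjects, within subjects, or pooled).

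Third, two further arguments against the slope should not be made. Assay error attenuates correlations as well as slopes. And although slopes for antibody and B-cell count are on different scales, the plan nowhere sets out to rank the two.

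Fourth, the intervals in Step 2 assume independent pairs, just as ±0.14 does, and could differ under a repeated-measures estimator. That is right, and it is why the target and the pairing must be fixed before the intervals are restated.

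**Conclusion.** The point holds as a mismatch between objective and analysis. The plan names a correlation and its precision as the goal, gives a model whose direct output is a unit-dependent slope, and omits the step between them. Because no time or group term is named, the choice left open can change the answer materially: 0.2 against 0.36 or 0.60 in the assumed illustration.

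The ±0.14 is a true worst case for 200 independent pairs. At the anticipated values the half-width is about 0.09 (r = 0.6) down to 0.003 (r = 0.99), so the figure is uninformative there rather than mistaken.

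A reader might also infer that the correlation analysis is underpowered, or that 200 subjects are too many because about 84 independent subjects would give a half-width of 0.14 at r = 0.6. Neither follows. The power claim reproduces, and the plan considers the group size separately for the comparisons between groups.

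The figures rest on Fisher's z, one pair per subject, and a two-sided 0.05 level for the power.

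**What to change.** In Section 12.0, define the target and its estimator:

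1. **Target.** Per serotype, on log-transformed values, the post-vaccination correlation of day-30 antibody with day-30 OPA, and of day-7 B-cell count with day-30 OPA. In the transplant groups, use the count from whichever day is selected as optimal. For Group 5 the matching samples are days 373 and 396. This agrees with the post-immunisation wording of Aims 2 and 3.
2. **Estimator.** Either a correlation of these single pairs with group accounted for, or a bivariate mixed model with time and group as fixed effects, naming which of its correlations is reported. Give a Fisher-z or subject-level bootstrap 95% CI. Adjusting the single-pair version for five groups costs four degrees of freedom: SE = 1/√(200 − 3 − 4) = 1/√193 = 0.0720, against 0.0712.
3. **Slope.** Keep the mixed-model slope as a secondary description.
4. **Precision.** State ±0.14 as the worst case near r = 0. Add the approximate intervals for 200 independent subjects: 0.50 to 0.68 at r = 0.6, 0.74 to 0.85 at 0.8 and 0.87 to 0.92 at 0.9. Note that they assume one pair per subject.

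The cost is SAP wording and slightly more modelling. No extra subjects, samples or visits are needed.

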We will measure TNFR expression by B cells following immunization with PCV13 in 65-75 year old RT and compare them to each of the groups described in Specific Aim 1. Gene expression, with focus on the B cell activating factor (BAFF) system, will be measured in PPS-specific and non-PPS specific B cells using single cell genomics and flow cytometry. These measures will be correlated with post-immunization functional antibody activity, a surrogate of protection.

Our central hypothesis is that the aging RT population responds poorly to PCV13 vaccination reflecting the combined effects of aging and RT. We postulate that both the number of memory B cells and expression of tumor necrosis factor (TNF) superfamily receptors, which play crucial roles in the response to pneumococcal polysaccharides (PPS), are deficient in the elderly RT population and contribute to poor pneumococcal vaccine responses.

We have developed fluorescently labeled PPS allowing us to study the nature and surface receptors of PPS-specific B cells. Our preliminary data demonstrate that RT recipients 1. Respond poorly to pneumococcal immunization as measured by antibody titer and functional antibody activity. 2. RT recipients and healthy elderly have lower absolute number of both IgM and switched memory B cells. 3. The number of PPS-specific IgM and switched memory B cells are significantly lower in RT recipients and 4. TACI and BAFF-R, members of the TNF superfamily receptors, expression is significantly lower in the PPS-specific memory B cells in the RT population versus healthy controls. The overall objective of this proposal is to characterize the immune response and explore possible mechanisms of poor vaccine responsiveness following immunization with PCV in the rapidly growing group of elderly with RT. As the RT population is a

heterogeneous group we will study only those in whom the underlying cause of renal failure is diabetes mellitus type 2 (DM2) and/or hypertension (HTN).

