certain Toll like receptors (TLR) play a crucial role in the immune response to pneumococcal vaccination [25, 26]. As shown in preliminary data, we have found decreased TACI and BAFFR expression in PPS-specific B cells derived from RT recipients. Although the number of RT recipients studied is very small, it was a consistent finding and merits further study. Adjuvants that specifically upregulate TACI expression, such as CpG-ODN, could therefore effectively increase immune responsiveness to pneumococcal vaccines. This strategy has shown to increase immune and memory responses to the conjugate pneumococcal vaccine in HIV-positive persons [27]. Our central hypothesis is that the elderly RT population responds poorly to PCV13 reflecting combined effects of aging and RT that result in abnormalities in both number of memory B cells and TNF superfamily expression, which play crucial roles in the response to polysaccharide antigens. We will test this hypothesis by measuring PPS-specific antibody and opsonophagocytic antibody responses, PPS-specific B cell phenotypes and surface and gene expression of the TNFR with known role in response to pneumococcal vaccination and correlate these individually with antibody and functional antibody responses. This has important clinical implications as deficient TNFR expression can be modulated by the addition of adjuvants such as CpG-ODN.

Preliminary Data

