4.0 Study Endpoints (if applicable)

The primary endpoint of this study is: quantify the antibody titers in mg/mL and opsonophagocytic antibody titer calculated as serum dilution, number of polysaccharide specific B cells, and absolute number of cells/mL induced by vaccination with PCV13.

Secondary endpoint of the study is to describe differences in gene expression of 56 genes to be determined by single cell PCR and comparing these between groups.

The primary safety endpoint of the study is measured as minimal versus moderate local side effect. Minimal side effect measured as no impairment in activity. Moderate local side effect is a side effect affecting use of the extremity for less than 24 hours.

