The vaccine(s) administered to the participants are FDA approved vaccinations and vaccination protocols. The standard and recommended dose of vaccine will be administered either by a qualified nurse or physician and both vaccines are considered low risk. In groups 1-4 PCV13 will be administered per standard of care and is not part of the experimental protocol. In group 5, both PPV23 and PCV 13 are not routine part of care and are part of the experimental protocol. These vaccines have however been extensively studied in this and other populations and are considered low risk and 70-80% protective against pneumococcal disease [30].

The risk associated with blood draws is minimal.

The data to be collected will be stored using an excel spread sheet. The data include:

-cause of end stage kidney disease if applicable

Date of kidney transplant

Complete blood count (CBC), comprehensive chemistry profile including renal and liver functions, HbA1c, serum albumin as measure of nutrition, HbsAg, HCV and HIV test

Pre- and post-immunization serum antibody titers and opsonophagocytic antibody titers to PPS14, 19A and 23F in ug/mL

IgM and switched memory B cell number and percentage

PPS+ B cell number and percentage

Serum BAFF concentration

Gene expression of the genes listed below in Table 4

#	GENE SYMBOL	GENE TITLE	PROTEIN FUNCTION	#	GENE SYMBOL	GENE TITLE	PROTEIN FUNCTION
Apoptosis				Lymphocyte signaling			
1	Bcl-2	B-cell lymphoma 2	Apoptotic suppressor	30	CBLB	E3 ubiquitin-protein ligase	Negatively regulates B cell Ag receptor signaling
2	Bcl-Xl (BCL1)	B-cell lymphoma-extra large	Apoptotic suppressor	31	FCRL2	Fc receptor like 2	Expressed in memory B cells in humans
3	Mcl-1	Induced myeloid leukemia cell differentiation protein Mcl-1	Apoptotic suppressor	32	CD1D	CD1D	Antigen presentation
4	BAX	BCL2-associated X protein	Pro-apoptotic function	33	CD200	OX2 membrane glycoprotein	Controls inflammation; immunosuppression
5	BAD	BCL2-associated agonist of cell death	Pro-apoptotic function	34	LAIR1	Leukocyte associated immunoglobulin like receptor 1	Inhibitor of B cell mediated signaling
6	BIM (BCL11)	BCL2-interacting mediator of cell death	Pro-apoptotic function	35	CD72	B cell differentiation antigen CD72	Negative regulator of B cell responsiveness
7	FAS	Fas cell surface death receptor	Apoptosis signaling	36	RFTN1	Raft linking protein	B cell antigen receptor mediated signaling

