23	PRDM1	PR domain zinc finger protein 1	Controls plasma cell differentiation	53	GPT2	Glutamic-pyruvic transaminase	Encodes mitochondrial alanine transaminase
24	XBP1	X-box binding protein 1	Controls late events of plasma differentiation	55			
25	Bcl6	B-cell CLL/Lymphoma 6	Transcription repressor required for GC formation antibody affinity maturation	55	ACTB	Actin beta	Conserved motif, ubiquitously expressed in all eukaryotic cells
26	Pax-5	Paired box-5	TF B cell lineage specific proteins				
27	IKZF3	Zinc finger protein Icos	TF B cell proliferation and differentiation				
28	SPIB	Spl-B Transcription factor	B cell development and antigenic stimulation				
29	FOXO1	Forkhead box o1	Plays a role in b cell differentiation				

Table 4. Gene expression to be studied by single cell PCR.

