Statistical Analysis Plan and Sample Size Justification for Aim 3

Aim 3 will examine differences in expression of TNFR markers (TACI, BCMA, and BAFF-R) using single cell qPCR on a subset of 10 participants (5 responders and 5 non-responders) from each of the 5 groups described in Aims 1 and 2 evaluated at baseline and 7 days post-vaccination. Single cell qPCR allows us to not only evaluate differences in expression between groups but also allows us to estimate the within subject and within group heterogeneity with great precision. Each participant sample provides between 40-96 viable cells that will be evaluated for gene expression at the single cell level. Relative fold-change in expression between participants who are 65-75 RT, 35-45 RT, or 65-75 DM/HTN with respect to the relevant controls will be evaluated using a linear mixed model approach. The model will include fixed effects for participant group, response status, and time and a random subject effect to account for repeated measurements resulting from individual cells from the same subject samples. Comparisons of number of gene expression between groups and within group between times will be evaluated using a series of contrasts from the LMM. For comparisons within group between responders and non-responders, a sample size of 5 responders and 5 non-responders with ≥ 40 cell level measures at 2 time points provides 80% power to detect 2.7 fold-increase or a 0.60 fold-decrease in expression using a two-sided test assuming within subject correlation of 0.5 and a Bonferroni corrected significance level (up to 10 comparisons) of $p = 0.005$. For comparisons between groups, we will have 10 subjects per group allowing us to detect even smaller fold-changes in expression.

All electronic data will be kept on the VA secure V drive or R drive and on MUSC secure Z drive that only team members will have access to.

13.0 Provisions to Monitor the Data to Ensure the Safety of Subjects (if applicable)

All adverse events (AE) will be reported and monitored through the data safety monitoring plan. The AE's will be characterized by: intensity/severity; expectedness; relatedness; frequency; outcome; treatment or action taken.

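### Table 4, the single-cell PCR gene list, names 53 of the stated 56 genes and none of TACI, BCMA or BAFF-R, the single-cell qPCR markers of Aim 3

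*Combined protocol and SAP*

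**What the plan says.** Section 1.0 sets the objective of Aim 3: "We will measure TNFR expression by B cells following immunization with PCV13". It adds that gene expression, concentrating on the BAFF system, will be measured "using single cell genomics and flow cytometry". Section 2.0 likewise plans "surface and gene expression of the TNFR with known role in response to pneumococcal vaccination".

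The Aim 3 part of section 12.0 names the markers and the assay: "Aim 3 will examine differences in expression of TNFR markers (TACI, BCMA, and BAFF-R) using single cell qPCR". It describes a linear mixed model with individual cells as repeated measures within subject. The subset is 10 participants per group, sampled at baseline and day 7, with 40 to 96 viable cells per sample. No other Aim 3 analysis is given.

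The gene list is in section 10.0, captioned "Table 4. Gene expression to be studied by single cell PCR". The list of data to be collected in the same section refers to it: "Gene expression of the genes listed below in Table 4". Section 4.0 gives the size of the panel; the secondary endpoint is to "describe differences in gene expression of 56 genes to be determined by single cell PCR".

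**The concern.** The SAP assigns three named receptors to an assay whose printed gene list contains none of them. TNF-superfamily receptor expression is half of the central hypothesis in section 1.0; the other half is memory B cell number. A laboratory that ordered its panel from Table 4 would produce single-cell data on apoptosis, cytokine, transcription-factor, signalling, immunoglobulin and metabolism genes, and none on the receptors that Aim 3 is about. The mixed model in section 12.0 would then have no outcome for its named markers.

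Section 4.0 does not close the gap. Its only expression endpoint is the 56-gene panel, and it lists no surface-receptor endpoint.

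**Working it through.** 1. **Count of named genes, against the plan's 56.** The left-hand column of Table 4 runs from 1 to 29 without a break: 29 genes. The right-hand column runs from 30 to 49 without a break: 20 genes. It then gives 51, 52 and 53 (3 genes) and ACTB (1 gene). Total: 29 + 20 + 3 + 1 = 53. Shortfall against section 4.0: 56 − 53 = 3. The stated 56 is not reproduced.

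2. **Numbering.** Numbers 50, 54 and 56 are unfilled. Number 55 is printed twice, once on an empty cell beside gene 24 and once for ACTB.

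3. **Search for the markers.** None of the 53 entries is TACI, BCMA or BAFF-R, either under those names or under their TNFRSF or CD aliases: 0 of 3 found. The nearest entries (FAS, TNFSF15, Siva1, TNF-alpha) are different genes. BAFF is not in the table either. The serum BAFF concentration in the data list is a different measurement and does not stand in for receptor expression.

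4. **Could the rows have been lost when the PDF was read?** The blocks where the receptors would be expected are numbered without gaps: cytokines and receptors (11 to 20) and lymphocyte signalling (30 to 42). All the irregularities lie in the right-hand column from 49 onwards. Number 50 falls between LDHA and COXII, inside the metabolism block. Five right-hand cells are empty: the one beside 24 and those beside 26 to 29. Loss is therefore unlikely for these genes, but not excluded.

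5. **Total after correction.** Let k (0 to 3) be the number of receptors among the three missing entries of a true 56-gene panel. Adding those not already in it gives 56 + (3 − k).
   - k = 3: 56 genes
   - k = 0: 59 genes
   - If the panel really has only the 53 printed genes, 53 + 3 = 56.

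6. **What would be run without the markers.** 5 groups × 10 participants × 2 time points = 100 samples. At 40 to 96 cells each, that is 4,000 to 9,600 cell-level profiles.

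7. **Does the power statement depend on the panel?** The significance level reproduces: 0.05/10 = 0.005. The 80% power does not, because no SD is stated. Solving backwards on the log2 scale with 5 per arm, SD = δ / [(z for two-sided 0.005 + z for 80%) × √(2/5)] = δ / 2.308.
   - 2.7-fold increase: 1.433 / 2.308 = 0.62
   - Decrease to 0.60: 0.737 / 2.308 = 0.32

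   No marker-specific quantity enters. The statement is a generic fold-change and would read the same for any gene.

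**The case against.** Five points can be made on the other side.

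- **The table may be incomplete only as printed.** With empty cells on the right and three numbers unfilled, entries may have been left blank in the source or lost in reading. This stands as a possibility. An unbroken left-hand column shows only that no whole row disappeared. The gaps are, however, in an unlikely place for these receptors.
- **The shortfall equals the number of receptors.** A reader might infer that the receptors are the three missing entries, so that adding them restores the stated 56. The documents do not support that. Nothing identifies the missing entries, and gap 50 sits among metabolism genes. If the inference were right, the fault would be only an incomplete printed table.
- **Aim 3 has a second method.** A reader might infer that the trial cannot answer Aim 3 at all. That goes too far. Sections 1.0 and 2.0 plan flow cytometry and surface expression, and section 10.0 assigns day 0 and day 7 samples to flow cytometry. The part without support is the single-cell qPCR. The flow route is itself unfinished: the data list names no surface-receptor variable, and the SAP gives no analysis of one.
- **The data list is not exhaustive.** It is worded as what the data include, and it omits adverse events, which section 13.0 says are recorded. So it does not forbid other genes. The caption of Table 4 still presents that table as the single-cell PCR list.
- **The power statement.** A reader might infer that the Aim 3 sample size was derived for these three markers and falls with them. It was not, as step 7 of the working shows.

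**Conclusion.** The concern holds for the single-cell qPCR part of Aim 3. On the text as supplied, sections 4.0, 10.0 and 12.0 disagree: 56 genes stated, 53 named, and 0 of the 3 Aim 3 markers among them. Running the panel as printed would leave the only Aim 3 analysis in the SAP without data on its named outcome.

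This is an inconsistency between parts of the plan, not evidence that the investigators chose to drop the receptors; sections 1.0, 2.0 and 12.0 all point to measuring receptor expression. The conclusion assumes that the printed Table 4 is the list the laboratory will use and that its text was read substantially intact. If the receptors are in the working panel, only the document needs correcting. The point should be settled before the 10-per-group subset is assayed.

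**What to change.** Before any single-cell assay is run:

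1. List TACI, BCMA and BAFF-R in Table 4, so that it agrees with the Aim 3 SAP.
2. Name these three as the Aim 3 outcome, separate from the wider panel that serves the secondary endpoint.
3. Fill or remove numbers 50, 54 and 56, correct the repeated 55, and restate the gene count in section 4.0: 56 if the receptors are the missing entries, up to 59 if they are other genes.
4. If flow cytometry is to contribute to Aim 3, add the surface-receptor variable to the data list and its analysis to section 12.0.

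The cost is a corrected table, short additions to the text and, if the receptors were truly left out, up to three added assays. No sample size changes, and the 0.005 level stays if the basis of up to 10 comparisons is kept.
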